# Figure 3-2 Clinical Status Evaluation (CSE) and Clinical Status Determination (CSD)

	Clinical Status Evaluation (CSE)											
D		Change since Day -42 (V101)										
Parameters	Better	Same	Worse									
6MWT	↑ 50m	$\Delta = \pm (<50) \mathrm{m}$	↓ 50m									
FVC	+10% relative $\Delta$	-15% < relative $\Delta$ < +10%	-15% relative $\Delta$									
FEV1	+10% relative $\Delta$	-15% < relative $\Delta$ < +10%	-15% relative $\Delta$									
MMRC dyspnea score	-1 point	No change	+1 point									

Clinical Status	Improved	Stable	Deteriorating
Determination	3 or more parameters	Does not meet criteria for	2 or more parameters "Worse"
(CSD)	"Better"	"Improved" or "Deteriorating"	or $\Delta$ MMRC is $\geq$ 2 points

### Figure 3-3 Patient pathway as determined by clinical status

### Figure 3-4 Steroid dose levels

### Incremental dose-steps of corticosteroid co-medication (mg/day):

14-15*
1

\* Prednisone (or equivalent) cannot be less than 2.5 mg/day or more than 15 mg/day during the Run-In and Treatment epochs.

### Treatment Epoch

A 16-week treatment epoch will commence on Day 1. Patients with a CSD of "deteriorating" at this visit will be ineligible to continue in the study. Patients with a CSD of "improved" or "stable" will decrease steroid dose by 1-step. (Note: Steroids will not be tapered below 2.5 mg/day) Then, the patients will be randomized to receive CMK389 or placebo, stratified by prior sarcoidosis immunosuppressant therapy (Stratum 1: azathioprine or Stratum 2: methotrexate).

During the treatment epoch, steroid dose will be guided by the results of CSE/CSD (Figure 3-3). During the treatment epoch, adverse events will be monitored on an ongoing basis. Monthly visits are scheduled to assess safety and efficacy. Physical exam, vital signs, blood draw (safety labs, pharmacokinetic [PK] samples, CCI ), spirometry, 6MWT, mMRC and CCI will be performed during the treatment epoch every 4 weeks or as described in the Assessment Schedule (Table 8-1).

Every effort should be put in place to adhere to this algorithm, but in cases where the Investigator feels that, during the Treatment Epoch, a subject's increase in steroids outside of the specified incremental dose-steps indicated or re-initiation of methotrexate or azathioprine is clinically indicated, this therapy can be started/adjusted. All the actual treatments should be reported in the CRF and all the PD parameters collected after therapy adjustment will be excluded from the primary analysis.

### Safety Follow-up Epoch

After the treatment epoch, the safety follow-up epoch will last 12 weeks. This enables the assessment of safety in adults with sarcoidosis for ~5 half-lives following the last administration of CMK389. During the safety follow-up epoch, physical exam, adverse events, safety labs, PK and CCI samples, CCI will be collected every four weeks. During the safety follow-up epoch, treatment for sarcoidosis will be guided by the Investigator; if necessary, methotrexate and/or azathioprine may be reintroduced and corticosteroid doses may be adjusted.

### Pregnancy Testing Period (WOCBP only)

Due to hypothetical effects on the fetus (see Section 3.2), WOCBP will be followed for an additional 8 weeks after EOS #1 (V399) (or 24 weeks total after their last treatment with CMK389) to ensure that they continue to use highly effective contraception.

# 3.2 Rationale for study design

The rationale for key elements of this study are as follows:

- Placebo controls: The placebo group is used to define the natural history of disease under the study's conditions. Comparison of placebo to the active group provides the most rigorous test of efficacy. Since no drugs are currently approved for the treatment of sarcoidosis, inclusion of a placebo arm is considered to be ethical; and the risk-benefit of placebo treatment is considered to be favorable. (Note: the potential benefits of alternative treatments, such as TNF inhibitors, are unproven/unknown, risk-benefit of alternative treatments are unfavorable, and such treatments are prohibited by this protocol).
- **Randomization:** Randomization is used to avoid "selection bias" in the assignment of subjects to treatment groups. Randomization also serves to balance the treatment groups with respect to many known and unknown confounding variables; and randomization forms the basis of assumptions for our statistical tests.
- **Blinding:** Conscious and unconscious biases are avoided ("detection bias" and "reporting bias", pertaining to outcome assessment) by ensuring that patients and investigators are unaware of treatment assignment.
- **Run-in epoch:** During this epoch, adjustments are made to background therapy in an effort to harmonize all the patients before commencement of the treatment epoch.
- **Discontinuation of methotrexate and azathioprine during the run-in epoch:** In clinical practice, immunosuppressants are often interrupted while the patient is closely observed for evidence of clinical change. This protocol mimics the immunosuppressant interruption that is frequently employed in clinical practice. This design allows a more robust evaluation of the efficacy of CMK389 while minimizing the potentially masking effects of immunosuppressant therapy.
- Steroid titration algorithm: Judicious titration of corticosteroids is common practice for a patient with sarcoidosis who is doing well; conversely, the dose of steroids is typically increased for a patient with sarcoidosis who is doing poorly. Within the context of this clinical trial, adjustment of steroids will be allowed. However, to avoid the introduction of "performance bias" by individual sites and investigators, all steroid titrations will be performed according to the rules of a pre-determined algorithm.

To prevent Addisonian crisis, steroids will not be tapered below a physiologic dose (2.5 mg/day); and steroid tapering will follow a very slow regimen, as per protocol.

• **Pregnancy Testing Period (WOCBP only):** IL-18 is expressed at the maternal-fetal interface (Tokmadzić et al 2002) and could potentially play a role, with other cytokines, in the pro-inflammatory events of early pregnancy such as ovulation, implantation decidual remodeling and placentation as well as contributing to the pro-inflammatory response promoting parturition (Laskarin et al 2005; Wilson et al 2004). However, there is also a pathogenic role of enhanced levels of pro-inflammatory cytokines, including IL-18, in

pregnancy, with reported links to preterm labor, recurrent abortion, intrauterine growth retardation, pre-eclampsia and spontaneous fetal resorption (El-Kabarity and Naguib 2011; Chau et al 2016). IL-18 knockout mice show no alteration in litter size, sex ratio, and weight gain and no structural abnormalities (Takeda et al 1998). IL-18 knockout mice develop hyperphagy, obesity and insulin resistance at 6 months of age (Netea et al 2006), which represents a theoretical risk to the neonate, although post-natal exposure to CMK389 through maternal transfer will be much shorter duration in humans relative to lifespan than in mice. Hence CMK389 treatment could have both positive and negative impacts on pregnancy. This represents a hypothetical risk to the developing fetus. Commercially Confidential Information

Therefore, WOCBP will be followed up to 24 weeks after their last treatment with CMK389 to ensure that highly effective contraception is used and fetal risks are avoided.

# 3.3 Rationale for dose/regimen, route of administration and duration of treatment

The selection of dose, 10 mg/kg, for CMK389 is based on identification of the "maximum feasible dose", Commercially Confidential Information

Additionally, based on the prediction of nonclinical modeling and simulation, monthly dosing at 10 mg/kg would have a near complete inhibition (>90%) of interferon gamma release in humans. Therefore, 10 mg/kg, the highest dose, is selected to maximize the chances for detecting efficacy in this proof-of-concept trial.

Monthly 10 mg/kg repeat-dosing is planned to achieve trough drug concentrations that are above (~50-fold) the EC80 (7.4 nM) of the in vitro whole blood assay for the inhibition of IFN-gamma release. Four monthly repeated doses of CMK389 at 10 mg/kg are anticipated to result in a peak concentration (~440  $\mu$ g/mL) Commercially Confidential Information

## 3.4 Rationale for choice of comparator

In this study, the placebo to CMK389 will be used as comparator to provide objective evidence of potential AEs and other safety data as well as clinical efficacy and PD data generated from patients exposed to CMK389.

# 3.5 Rationale for choice of background therapy

There are no FDA/EMA-approved therapies for sarcoidosis. It is common practice for patients to be treated with non-specific immunosuppressants: corticosteroids, with or without the

addition of a cytotoxic agent (such as methotrexate, azathioprine, or hydroxychloroquine). Due to potential confounding factors and the absence of proven efficacy, methotrexate and azathioprine will be discontinued during the run-in epoch. However, corticosteroid medications and hydroxychloroquine will be allowed as background therapy during this study, in order to test the efficacy of CMK389 in a "real-world" setting.

# 3.6 Purpose and timing of interim analyses/design adaptations

Commercially Confidential Information

# 3.7 Risks and benefits

### Potential benefit:

• There is no proven direct medical benefit for subjects who will participate in this study. However, the patient's participation in this study will facilitate and advance research in the field of drug development for the treatment of sarcoidosis, which is still a significant unmet medical need (Section 1.1).

## Potential risk:

•

Commercially Confidential Information

• Based on clinical observation: Commercially Confidential Information

Therefore, to date, no

specific risks have been identified through clinical observation.

- **Based on mechanism of action (i.e., drug class):** CMK389 is an immunosuppressant; therefore patients undergoing treatment with CMK389 are theoretically at risk for infection. CMK389 is a biologic compound; therefore patients who receive CMK389 are theoretically at risk of acute infusion and/or hypersensitivity reactions.
- Based on COVID-19 pandemic: CMK389 has been shown to selectively bind to IL-18 and potently inhibit IL-18 activity. Blocking IL-18 may impair the innate and cytotoxic immune responses that play a role in viral clearance. IL-18 contributes to antiviral immune responses by promoting IFN-γ production by T cells, natural killer cells, and natural killer T cells and supports the induction of cytotoxic T cells. Impaired cytotoxic T cell responses may impair the killing of virus-infected cells. However, data generated to-date to assess the impact of CMK389 on immune function support a lack of a broad immunosuppressive effect.

CMK389 is not expected to impair the production of viral-specific antibodies, including those against SARS-CoV-2. The inflammasome and the pivotal mediators IL-1 $\beta$ , IL-18, and NLRP3 contribute to the hyper-inflammatory response that results in severe pulmonary tissue damage after initial SARS-CoV and SARS-CoV-2 infections. Patients with severe COVID-19 and respiratory failure have elevated levels of IL-1 $\beta$  and its downstream cytokine IL-6, as well as IFN- $\gamma$  and CCI , both downstream markers of IL-18 pathway activation. Hence, blocking IL-18 with CMK389 could theoretically play a protective role in suppressing the hyper-inflammatory response to these viruses.

Novartis is committed to supporting the safety and well-being of our study participants, investigators, and site staff. All local regulations and site requirements should be applied in the countries that are affected by the COVID-19 pandemic. The Novartis clinical trial team will review the situation in each participating country and work with Investigators to continue to ensure the safety of participants during the conduct of the trial. A benefit/risk assessment has been made and has been determined to not significantly change for the participants that are planned to be enrolled in the proposed clinical trial. As the COVID-19 situation evolves, Investigators must use their best judgement to minimize risk to participants during the conduct of the study.

### **Risk mitigation strategy:**

- The risk to subjects in this trial will be minimized by adherence to the eligibility criteria, close clinical monitoring, and compliance with criteria for treatment interruption outlined in the protocol (Section 7.2).
- Drug-drug interactions are unlikely with biologics, however, sites and patients must strictly observe and adhere to the list of prohibited medications listed in the protocol (Section 5.2).
- Women of childbearing potential must be informed that taking the study treatment may involve unknown risks to the fetus if pregnancy were to occur during the study; and agree that, in order to participate in the study, they must adhere to the contraception requirements outlined in Section 4.2 (Exclusion Criteria). If there is any question that the subject will not reliably comply, they should not be entered into or continue in the study.
- Patients with current, active or latent infection are excluded from this study. In addition, investigators will remain vigilant for signs of intercurrent infections (i.e., nausea, vomiting, fever, rash, confusion, or muscle aches).

### **Risk of Imaging Procedures:**

The total radiation effective dose in this protocol will be less than 15 mSv; 4 mSv from HRCT scanning and 11 mSv from [F]FDG-PET/CT scans, including attenuation correction scans. In large and obese patients, a higher injected [F]FDG activity may be required but the total radiation exposure in these patients will not exceed 20 mSv. This amount of radiation is considered to be a moderate risk, category III (ICRP 1991) and is balanced against the substantial societal benefit gained from the trial.

### Miscellaneous:

There may be unknown risks of CMK389 which may be serious.

### 3.7.1 Blood sample volumes

A maximum of 493 mL of blood is planned to be collected over a period of 9 months, from each subject as part of the study. Additional samples may be required for safety monitoring.

Timings of blood sample collection are outlined in the Assessment schedule (Section 8.1).

A summary blood log is provided in the Site Operations Manual (SOM). Instructions for all sample collection, processing, storage and shipment information is also available in the SOM and Central Laboratory Manual.

See Section 8.9 regarding the potential use of residual samples.

# 4 Population

The investigator must ensure that all subjects being considered for the study meet the below eligibility criteria. No additional criteria should be applied by the investigator in order that the study population will be representative of all eligible subjects.

Subject selection is to be established by checking through all eligibility criteria at screening. A relevant record (e.g., checklist) of the eligibility criteria must be stored with the source documentation at the study site prior to randomization.

Deviation from any entry criteria excludes a subject from enrollment into the study.

No additional exclusions may be applied by the investigator, in order to ensure that the study population will be representative of all eligible patients.

## 4.1 Inclusion criteria

Subjects eligible for inclusion in this study must fulfill **all** of the following criteria:

- 1. Written informed consent must be obtained before any assessment is performed
- 2. Male and female subjects ages 18-75 years of age inclusive at screening
- Subjects must have a body mass index (BMI) at screening within the range of 18 46 kg/m^2. BMI = Body weight (kg) / [Height (m)]
- 4. Pulmonary Sarcoidosis present > 1 year prior to screening with a historical biopsy (from any organ or body part) confirming diagnosis prior to screening

- 5. Scadding stage II, III or IV as determined by the most recent chest x-ray obtained within 12 months prior to screening or at screening (confirmed by the investigator)
- 6. HRCT extent of fibrosis <20% (confirmed by the central imaging reader) on an HRCT obtained within 12 months prior to screening or at screening
- 7. Treatment with 5-15 mg/day prednisone (or prednisone oral equivalents) for
   ≥ 6 consecutive months prior to screening and with a minimum of 80% compliance with
   treatment each month as determined by the investigator.
- Co-medication with methotrexate or azathioprine for ≥ 6 months prior to screening and with a minimum of 80% compliance with treatment each month as determined by the investigator (Note: hydroxychloroquine is allowed as background therapy but not required)
- Able to perform reliable, reproducible pulmonary function test maneuvers per American Thoracic Society/European Respiratory Society (Culver et al 2017; Miller et al 2005; Graham et al 2017) guidelines
- 10. Able to communicate well with the investigator, to understand and comply with the requirements of the study

# 4.2 Exclusion criteria

Subjects fulfilling any of the following criteria are not eligible for inclusion in this study:

- 1. History of hypersensitivity to the study drug, or to drugs of similar chemical classes (i.e., IgG-1 related biologic agents)
- 2. Diagnosis of significant pulmonary hypertension (WHO group 5) requiring pharmacological treatment
- 3. Active cardiac sarcoidosis requiring treatment. Inactive cardiac sarcoidosis or stable cardiac sarcoidosis not requiring treatment are permissible.
- 4. A known diagnosis of neurosarcoidosis
- 5. Forced vital capacity (FVC) <50% of predicted at screening (central read)
- 6. Modified British Medical Research Council (mMRC) dyspnea scale  $\geq$  3 at screening
- 7. Concomitant treatment with leflunomide, cyclophosphamide, mycophenolate, infliximab, etanercept, adalimumab, golimumab, ustekinumab, roflumilast, pentoxifylline, and abatacept within 12 weeks of screening
- 8. Any prior treatment with rituximab, canakinumab, anakinra, and tocilizumab
- 9. Use of other investigational drugs within 5 half-lives of screening, or until the expected PD effect has returned to baseline, whichever is longer; or longer if required by local regulations
- 10. Current use of any inhaled substance, including but not limited to tobacco, marijuana products and the use of any electronic cigarette or vaping device (note that respiratory inhalers or nebulizers for delivery of prescribed medication for pulmonary sarcoidosis are allowed).
- 11. Any conditions or significant medical problems which, in the opinion of the investigator and in consultation with the sponsor, immunocompromises the patient and/or places the patient at unacceptable risk for immunomodulatory therapy
- 12. Any one of the following screening values of complete blood count laboratory values:

- Hemoglobin levels below 8.0 g/dL
- Total leukocyte count less than  $2,000/\mu$ L
- Platelets <100.0 x 10^9/L
- Absolute neutrophil count (ANC)  $< 1.5 \times 10^9/L$
- 13. Active viral, bacterial or other infections requiring systemic treatment at the time of screening, or within 3 months from screening in case of a known or suspected COVID-19 infection, unless resolution is confirmed radiographically as determined by the Investigator.
- 14. History of primary or secondary immunodeficiency, or a positive Human Immunodeficiency Virus (HIV) (Enzyme-linked Immunosorbent Assay (ELISA) and Western blot) test result at screening
- 15. Positive hepatitis B surface antigen (HBsAg) with concurrent negative hepatitis B surface antibody (anti-HBs); or positive total hepatitis B core antibody (anti-HBc) with concurrent negative anti-HBs; or positive hepatitis C antibody (anti-HCV) unless it can be documented that the patient has received highly-effective HCV-specific antiviral therapy, HCV RNA levels are measured, and HCV RNA is undetectable at least 12 weeks after the conclusion of HCV-specific antiviral therapy; i.e., any acute or chronic infection with hepatitis B or hepatitis C
- 16. Evidence of active or latent tuberculosis (TB) infection, as determined by Quantiferon test at screening (Note: if Quantiferon test is indeterminate, it may be repeated once. Two indeterminate Quantiferon tests will be considered as evidence of TB infection. Furthermore, after anti-TB treatment, patients with history of or latent TB may become eligible according to national guidelines)
- 17. Receipt of live/attenuated vaccine within a 1 month period before first dose of CMK389 (V201)
- 18. Contraindication to FDG-PET scan investigations such as severe claustrophobia or uncontrolled diabetes
- 19. History of confirmed malignancy of any organ system (other than localized carcinoma of the skin (for example: basal, squamous) or in situ cervical carcinoma), treated or untreated, within 5 years of screening, regardless of whether there is evidence of local recurrence or metastases
- 20. Pregnant or nursing (lactating) women, where pregnancy is defined as the state of a female after conception and until the termination of gestation, confirmed by a positive hCG laboratory test
- 21. Women of childbearing potential (WOCBP) (see definition below), unless they are using highly effective methods of contraception during dosing and for an additional 6 months after the last dose (infusion)

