#### 8.4.4 **Hepatitis and HIV Screen**

All subjects will be screened for HIV, Hepatitis B and C. See the SOM for details.

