# 15 Appendix 1: Liver Event Definitions and Follow-up Requirements

Definition	Thresholds
Potential Hy's law cases	
 
ALT or AST > 3 × ULN and TBL > 2 × ULN without initial increase in ALP to > 2 × ULN
 

ALT or AST elevation with coagulopathy	
 
ALT or AST > 3 × ULN and INR > 1.5 (in the absence of anticoagulation)
 

ALT or AST elevation accompanied by symptoms	
 
ALT or AST > 3 × ULN accompanied by (general) malaise, fatigue, abdominal pain, nausea, or vomiting, or rash, or eosinophilia
 

Isolated ALT or AST elevation	• ALT or AST > 8 × ULN
	• $5 \times ULN < ALT/AST \le 8 \times ULN$
	• $3 \times ULN < ALT/AST \le 5 \times ULN$
Isolated ALP elevation	
 
ALP > 2 × ULN (in the absence of known bone pathology)
 

Others	Any clinical event of jaundice (or equivalent term)
	Any adverse event potentially indicative of liver toxicity

Criteria	Actions required
Potential Hy's Law case ALT or AST elevation with coagulopathy ALT or AST elevation accompanied by symptoms Isolated ALT or AST elevation > 8 × ULN Jaundice	
 
Discontinue the study treatment immediately
 
Hospitalize, if clinically appropriate
 
Establish causality
 
Complete CRFs per liver event guidance*
 

Isolated ALT or AST elevation > 5 to ≤ 8 × ULN	
 
If confirmed, consider interruption or discontinuation o study drug
 

	
 
If elevation persists for more than 2 weeks, discontinue the study drug
 

	Establish causality
	
 
Complete CRFs per liver event guidance*
 

Isolated ALT or AST elevation > 3 to ≤ 5 × ULN (patient is asymptomatic)	Monitor liver chemistry tests two or three times weekly
Isolated ALP elevation	Repeat liver chemistry tests within 48-72 hours
	
 
If elevation is confirmed, measure fractionated ALP; if >50% is of liver origin, establish hepatic causality
 

	Complete CRFs per liver event guidance*
Any AE potentially indicative of liver toxicity	
 
Consider study treatment interruption or discontinuation
 

	Hospitalize if clinically appropriate
	
 
Complete CRFs per liver event guidance*
 

\*Liver event guidance for CRF completion is available in the Site Operations Manual

Disease	Assessment
Hepatitis A, B, C, E	
 
IgM anti-HAV; HBSAg, IgM anti-HBc, HBV DNA; anti- HCV, HCV RNA, IgM & IgG anti-HEV, HEV RNA
 

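### Exclusion criterion 15 gives two answers for a subject positive for both hepatitis B surface antigen and surface antibody: its test conditions do not match its own closing words or section 3.7

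*Protocol*

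**What the plan says.** Protocol section 4.2, criterion 15, sets two test conditions for hepatitis B. The first is "Positive hepatitis B surface antigen (HBsAg) with concurrent negative hepatitis B surface antibody (anti-HBs"). The second is "positive total hepatitis B core antibody (anti-HBc) with concurrent negative anti-HBs". A hepatitis C condition follows, and the criterion then sums itself up: "i.e., any acute or chronic infection with hepatitis B or hepatitis C".

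Section 3.7 makes a related statement under risk mitigation: "Patients with current, active or latent infection are excluded from this study". Under potential risk, the same section gives the reason for caution: "CMK389 is an immunosuppressant; therefore patients undergoing treatment with CMK389 are theoretically at risk for infection".

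On procedure, section 8.4.4 says only: "All subjects will be screened for HIV, Hepatitis B and C. See the SOM for details". Table 8-1 places that screen at the screening visit and nowhere else. Section 4 adds: "No additional exclusions may be applied by the investigator".

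**The concern.** The summary at the end of criterion 15 is introduced as a restatement of the tests before it, so the tests should pick out the same patients as the summary. They may not. A positive anti-HBs result switches off both hepatitis B conditions, including the one built on the surface antigen, whereas the summary and section 3.7 have no such switch.

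Three things are at stake:

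- **Safety.** A subject with a positive surface antigen could be judged eligible for four infusions of a drug that the protocol classes as an immunosuppressant, on top of prednisone.
- **Uniform eligibility.** Sites, and the monitors who must verify entry criteria under section 10.1, need one answer per patient.
- **Attribution.** If a liver event followed, hepatitis B is among the alternative causes that Table 15-3 asks the site to rule out.

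**Working it through.** No alpha, power, effect size or sample size enters this point, and the plan states no figure to reproduce. The check is to apply the written rule to every possible serology pattern.

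**Rule, from criterion 15.** Excluded on hepatitis B tests = (HBsAg positive and anti-HBs negative) or (anti-HBc positive and anti-HBs negative).

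| HBsAg | anti-HBs | anti-HBc | Excluded by the test conditions |
|---|---|---|---|
| + | + | + | No |
| + | + | − | No |
| + | − | + | Yes |
| + | − | − | Yes |
| − | + | + | No |
| − | + | − | No |
| − | − | + | Yes |
| − | − | − | No |

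- Patterns excluded: 3 of 8, all with anti-HBs negative. One of the three is HBsAg negative and is caught by the anti-HBc condition alone.
- HBsAg-positive patterns: 4. Excluded: 2. Not excluded: 4 − 2 = 2, both with anti-HBs positive, whatever the anti-HBc result.

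These are counts of logical patterns, not probabilities.

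**The same HBsAg-positive, anti-HBs-positive subject under each text.**

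- Test conditions of criterion 15: not excluded.
- Closing words of criterion 15: excluded if the site regards the subject as having acute or chronic hepatitis B. Anti-HBs is not mentioned.
- Section 3.7 risk mitigation: excluded if the site regards the subject as infected. Anti-HBs is again not mentioned.

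**Is the conflict settled elsewhere?**

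- Criterion 11 (conditions that immunocompromise the patient or make immunomodulatory therapy too risky) rests on the investigator's opinion in consultation with the sponsor.
- Criterion 13 reaches only active infections that need systemic treatment.
- Criterion 26 (conditions that may put the subject in jeopardy) is again a case-by-case judgement with the sponsor.
- The protocol names no HBV DNA test for entry. The hepatitis C condition, by contrast, calls for RNA results before a treated antibody-positive subject may enter.
- Section 8.4.4 gives no decision rule and refers to the Site Operations Manual, which was not available.

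None of these gives a fixed answer for the pattern in question.

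**The case against.** A reader might infer that the protocol lets surface-antigen-positive patients through to dosing. The documents do not support that, for several reasons.

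- The closing words are part of the exclusion criterion. A site that reads the whole of criterion 15 can exclude the subject on them.
- Section 4 bars added exclusions, but it does not bar the use of listed ones. Criteria 11, 13 and 26 remain open to the investigator.
- Monitoring is not absent after entry. Clinical chemistry, with ALT, AST and bilirubin, is taken at every dosing and follow-up visit. Section 9.3 sends a liver event to the work-up in Table 15-3, which includes "HBSAg, IgM anti-HBc, HBV DNA". Hepatitis B testing after screening is therefore conditional on a liver event rather than missing.
- Table 15-3 lists assays for a work-up. It is not an eligibility rule, and its silence on anti-HBs does not contradict criterion 15.
- Section 3.7 is a general summary. It is already looser than the operative criteria: criterion 16 lets patients with latent tuberculosis become eligible after treatment. The same section also says that data so far point away from a broad immunosuppressive effect.
- No passage says that HBsAg and anti-HBs positive together mean infection.

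All of this stands, and it limits the point to an inconsistency. It does not remove it. The backstops are discretionary or partial, liver monitoring acts after entry, and the mismatch between the tests and the closing words lies within criterion 15 itself, whatever weight section 3.7 is given.

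**Conclusion.** The point holds as an internal inconsistency in a safety exclusion. Two of the four HBsAg-positive patterns meet neither hepatitis B test condition, while the words meant to summarise those conditions contain nothing that would let them pass. A site applying the tests and a site applying the closing words can decide differently on the same subject.

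The conclusion assumes that the test conditions are read literally and that the Site Operations Manual does not settle the matter. The further step, that the closing words would catch such a subject, relies on the ordinary meaning of a positive surface antigen, which the documents do not spell out.

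The number of subjects affected cannot be estimated, because the documents give no frequency for the pattern. With about 66 subjects to be randomised it may be few or none. Sample size, power and the primary analysis are unaffected. The case for acting is that the rule protects patients and the correction is small.

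**What to change.** Amend criterion 15 so that its hepatitis B test conditions, its closing words and the section 3.7 statement agree, and so that together they give one answer for an HBsAg-positive, anti-HBs-positive subject. Which answer that should be is a clinical matter for the sponsor. The hepatitis screening instructions in the Site Operations Manual should be checked against the amended text.

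The cost is a wording change in a protocol amendment. HBsAg, anti-HBs and anti-HBc results are already needed to apply the criterion, so reconciling the text requires no new test. Depending on what the sponsor decides, an occasional screening outcome may change.
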